9.4.4 Method of Assigning Subjects to Treatment Groups

Subjects willing and eligible to participate in this study will be assigned to a treatment cohort according to the assignment list. Assignment to the 2nd dose cohort will start after all subjects for the 1st dose cohort are enrolled. The detailed process of subject identification and assignment of subject numbers can be found in section 9.4.10.2. No randomization is planned for this study.

9.4.5 Selection of Doses in the Study

The doses selected in this study represent immunogenic dose levels as observed in prior clinical trials using MVA-vector-based vaccines.

9.4.6 Selection and Timing of Dose for Each Subject

All dosing events will occur between 8:00 h and 14:00 h.

9.4.7 Blinding

As this is an open-label study, no blinding procedures are necessary.

9.4.8 Prior and Concomitant Therapy

As only healthy subjects will be enrolled, concomitant use of any medicinal product is forbidden prior to dosing as defined in section 9.3.2 *Exclusion Criteria* of this protocol. Prior to the dosing, subjects will be asked about this point.

Any use of drugs will be documented specifying the substance, dose, time and reason for use.

9.4.9 Rescue Medication

For symptomatic management of flu-like symptoms, the use of anti-pyretic drugs (e.g. paracetamol/ibuprofen) within the daily recommended dosage will be allowed after consultation of the investigator.

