8.2 Primary Endpoints

The safety, tolerability, and reactogenicity of the experimental vaccine MVA-MERS-S will be measured as followed:

- Occurrence of solicited local reactogenicity signs and symptoms for 14 days following the vaccination (see Table 3)
- Occurrence of solicited systemic reactogenicity signs and symptoms for 14 days following the vaccination (see Table 4 and Table 5)
- Occurrence of unsolicited AEs for 28 days following the vaccination
- Change from baseline of safety laboratory measures
- Occurrence of SAEs throughout the study period

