9.3.2 Exclusion Criteria

Subjects are excluded from the study if any of the following criteria are met at screening or at day -1:

1. Prior receipt of a MERS vaccine or MVA immunizations.
2. Receipt of any vaccine in the 2 weeks prior to 1st trial vaccination (4 weeks for live vaccines) or planned receipt of any vaccine in the 3 weeks following the 2nd trial vaccination.
3. Known allergy to the components of the MVA-MERS-S vaccine product as eggs, chicken proteins, and gentamycin or history of life-threatening reactions to vaccine containing the same substances.
4. Known history of anaphylaxis to vaccination or any allergy likely to be exacerbated by any component of the trial vaccine.
5. Participation in a clinical trial or use of an investigational product within 30 days or five times the half-life of the investigational drug -whichever is longer- prior to receiving the first dose within this study.
6. Evidence in the subject's medical history or in the medical examination that might influence either the safety of the subject or the absorption, distribution, metabolism or excretion of the investigational product under investigation.
7. Clinically relevant findings in ECG, in particular prolonged QTc (B) of > 450 msec in males and > 460 msec in females.
8. Any positive result for HIV1/2, HCV antibody or HBs antigen testing.
9. Any confirmed or suspected immunosuppressive or immunodeficient condition, cytotoxic therapy in the previous 5 years, and/or diabetes.
10. Subjects with inflammatory, infectious and neuroinflammatory underlying disease which could cause an expected impairment of the blood brain barrier such as meningitis, multiple sclerosis, epilepsy, or Alzheimer's disease.
11. Any chronic or active neurologic disorder, including seizures, and epilepsy, excluding a single febrile seizure as a child.
12. Known history of Guillain-Barré Syndrome.
13. Active malignancy or history of metastatic or hematologic malignancy.
14. Suspected or known alcohol and/or illicit drug abuse within the past 5 years.
15. Moderate or severe illness and/or fever >38°C within 1 week prior to vaccination.
16. Administration of immunoglobulins and/or any blood products within the 120 days preceding study entry or planned administration during the study period. Oral or parenteral immunosuppressant and immunomodulating agents (including interferons) should be discontinued at least 4 weeks prior to first injection.

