17. History of blood donation within 60 days of enrollment or plans to donate within the treatment phase (until the 2nd vaccination).
18. Receipt of chronic (defined as more than 14 days) immune suppressants or other immune-modifying drugs within 6 months of study inclusion (screening).
 - For corticosteroids, this will mean prednisone, or equivalent, greater than or equal to 0.5 mg/kg/day.
 - Intranasal and inhaled steroids are allowed. Topical steroids are permitted provided they are not required to be applied to injection site.
19. Subjects with skin lesions close to the injection site or active oral lesions will be excluded.
20. Thrombocytopenia, contraindicating intramuscular vaccination based on investigator's judgment.
21. Subjects with a significant infection or known inflammation.
22. History of relevant cardiovascular disorders or evidence of hyper- (sitting blood pressure systolic >140 or diastolic >90 mmHg) or hypotension (sitting blood pressure systolic <90 or diastolic <40 mmHg) at screening.
23. Subjects who are known or suspected not to comply with the study directives.

24. Any other significant finding that in the opinion of the investigator would increase the risk of the individual having an adverse outcome from participating in this study.

Additional criteria for the subjects receiving the 3rd vaccination:

Receipt of any vaccine in the 2 weeks prior to (4 weeks for live vaccines) or 3 weeks following the 3rd vaccination.

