9.3.2.1 Reproductive Potential

The study population includes female of child-bearing potential (FOCP). FOCP have to agree to comply with the applicable contraceptive requirements of the protocol as named below for the duration of the study or females who are permanently sterilized (at least 6 weeks post-sterilization).

Effective contraception is defined as a contraceptive method with failure rate of less than 1% per year when used consistently and correctly and when applicable, in accordance with the product label for example:

- Oral contraceptives, either combined or progesterone alone,
- injectable progesterone,
- implants of etonogestrel or levonorgestrel
- oestrogenic vaginal ring
- percutaneous contraceptive patches,
- intrauterine device or intrauterine system,
- male partner sterilization at least 6 months prior to the female subject's entry into the study, and a monogamous relationship
- male condom combined with a vaginal spermicide (foam, gel, film, cream or suppository).
- male condom combined with a female diaphragm, either with or without a vaginal spermicide (foam, gel, film, cream, or suppository)

Condoms are to be used with the mentioned acceptable contraceptives.

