9.5.2.8.9 Reactogenicity

To assess reactogenicity after each immunization body temperature and reaction are recorded for at least 14 days after vaccination or until any symptoms resolved if longer. According to the defined time frame of ± 2 days for the ambulatory visit on day 42 recording might be shortened to day 40. During confinement at the study ward temperature and solicited injection site and systemic reactions will be assessed and recorded by a designated member of the study team. After dismissal subjects are asked to maintain a diary to record daily temperature and solicited (expected) injection site and systemic reactions for 14 days after each dosing. Subjects will be asked to maintain a second diary for another 14 days to record medicinal events. As described above, the second diary after the second immunization should be maintained at least until day 40. Subjects will be trained on the thermometer and diary use.

The following items will be recorded:

- Daily temperature (incl. the method by which it was taken)
- Daily measurement of intensity grade of all other solicited (expected) injection site and systemic reactions
- Action taken for each recorded event (none, medication taken, physician consulted, hospitalization)

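### Antipyretics are allowed in the 14-day solicited window, but the diary items do not tie the daily temperature to drug intake, so later fever, its peak and its duration can be understated

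*Protocol*

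**What the plan says.** **Permission.** Section 9.4.9 opens with its purpose, "For symptomatic management of flu-like symptoms", and then says "the use of anti-pyretic drugs (e.g. paracetamol/ibuprofen) within the daily recommended dosage will be allowed after consultation of the investigator". It gives no start or stop day.

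**Endpoint.** Section 8.2 lists among the primary endpoints "Occurrence of solicited systemic reactogenicity signs and symptoms for 14 days following the vaccination". Section 9.7.1 names fever, chills, myalgia, arthralgia, fatigue and headache as separate solicited events.

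**Temperature.** On the ward, temperature is taken at 0, 2, 4, 6, 8, 12 and 24 hours (Table 2a). After discharge, the diary items in 9.5.2.8.9 are "Daily temperature (incl. the method by which it was taken", the daily intensity of other solicited reactions, and the action taken for each recorded event. No reading time is listed, and no order relative to drug intake.

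**Drug records.** Section 9.4.8 requires substance, dose, time and reason for any drug used.

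**Before dosing.** Section 9.4.8 also says "concomitant use of any medicinal product is forbidden prior to dosing as defined in section 9.3.2". The medicines restricted in 9.3.2 are vaccines, investigational products, immunoglobulins and blood products, cytotoxic therapy, and immune-modifying agents, for example "Oral or parenteral immunosuppressant and immunomodulating agents (including interferons) should be discontinued at least 4 weeks prior to first injection". No analgesic or antipyretic is named.

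**Interim report.** Sections 9.10 and the Synopsis list its content as adverse events, vital signs, ECGs and laboratory data. Antipyretic use is not listed.

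**The concern.** Paracetamol and ibuprofen act on several solicited items at once. A subject may take one for headache or chills and later that day read 37.6 °C. The headache or chills is recorded, but a fever that the drug prevented is not. Because the action-taken item belongs to a recorded event, no medication entry appears against fever either. A drug time exists elsewhere in the record, but without a time for the temperature nobody can tell whether that reading was a treated one.

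Grade and duration matter beyond description. Table 4 separates Grade 3 from Grade 4 fever above 40.0 °C by whether it lasts 24 hours. The systemic holding rule in 9.3.3.3 counts only reactions that persist at Grade 3 or above for more than 48 to 72 hours. Section 7.3 describes reactions to MVA vaccines as dose-dependent. Symptom-driven drug use could therefore be more frequent at 10^8 than at 10^7 pfu, and any understatement could then be larger there.

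**Working it through.** No figure in the protocol depends on this point: section 9.8.2 uses no formula and no reaction rate. The check is therefore of the text, followed by an illustration on assumed values.

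**1. How much of the window rests on the diary.** Subjects leave the ward on post-dose day 1 after doses 1 and 2. Days 2 to 14 are 13 days. Taking visits on their nominal days:

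- Dose 1: visits on days 3, 7 and 14, so 13 − 3 = 10 diary-only days.
- Dose 2: visits on study days 35 and 42 (post-dose days 7 and 14), so 13 − 2 = 11 diary-only days.
- Dose 3: visits on days 1, 3, 7 and 14, so again 13 − 3 = 10 of days 2 to 14.

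On these days the diary is the only scheduled temperature source.

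**2. What survives treatment in the record.**

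| Quantity | Captured when an antipyretic is taken? |
|---|---|
| Symptom that prompted the drug | Yes, with action taken |
| Drug, dose, time, reason | Yes (9.4.8) |
| Fever beginning after intake | Not if the drug keeps the reading below 38.0 °C |
| Peak grade and duration of fever | Only as seen under treatment |
| Whether a diary temperature preceded or followed intake | Not derivable from the listed items |

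An analysis plan cannot restore the last row if the reading time was never collected.

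**3. Illustration: dose contrast.** The inputs are assumptions, not protocol figures: true rates of 20% at the lower dose and 50% at the higher, with masked shares mL and mH.

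Observed difference = 0.50(1 − mH) − 0.20(1 − mL)

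| mL | mH | Observed difference |
|---|---|---|
| 0 | 0 | 0.50 − 0.20 = 30 points |
| 10% | 10% | 0.45 − 0.18 = 27 points |
| 10% | 30% | 0.35 − 0.18 = 17 points |
| 10% | 50% | 0.25 − 0.18 = 7 points |

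The large reductions come from assuming unequal masking. With equal masking of 10% the difference barely moves.

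**4. Illustration: systemic holding rule.** More than 25% of injections means at least 4 of 12 or at least 7 of 24. Let p be the assumed true rate of qualifying reactions, and m the share that treatment lowers or shortens until it no longer qualifies. Injections are treated as independent.

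P(trigger) = P(X ≥ r), X ~ Binomial(n, p(1 − m))

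| n, r | p | m = 0 | 10% | 30% | 50% |
|---|---|---|---|---|---|
| 12, 4 | 20% | 0.205 | 0.155 | 0.075 | 0.026 |
| 12, 4 | 40% | 0.775 | 0.680 | 0.445 | 0.205 |
| 24, 7 | 20% | 0.189 | 0.126 | 0.041 | 0.007 |
| 24, 7 | 40% | 0.904 | 0.818 | 0.526 | 0.189 |

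Section 7.3 reports only mild-to-moderate events with MVA vaccines, so these values of p are probably high. The table shows the direction of the effect, not a forecast.

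**5. Before dosing.** Read alone, 9.4.8 forbids every medicine. Read through its cross-reference, it forbids only what 9.3.2 names. The literal reading cannot be intended, because 9.3.2.1 accepts "Oral contraceptives, either combined or progesterone alone" and 9.3.2 allows inhaled and intranasal steroids. Subjects are asked about medicines before dosing, but no criterion says how a report of analgesic use is to be handled.

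**The case against.** The strongest reply is that the protocol already holds most of what is needed. Drug time and reason are mandatory. Concomitant medication is asked about at each post-dose visit, and on the ward alongside staff-measured temperatures. The endpoint is occurrence, and treatment is allowed for symptoms already present, so the prompting symptom counts. Table 5 also grades subjective fever. The diary form is not shown, and 9.5.2.8.9 may not list every field. How treated readings are analysed can be left to the SAP.

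Much of this stands, and it rules out several stronger readings that a reader might infer:

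- **That systemic reactions as a whole are under-counted.** The exposed part is later measured fever, its peak grade and its duration.
- **That a suppressed fever leaves no trace.** The drug record is a trace. What is missing from the listed items is the reading time needed to link it to the temperature.
- **That the safety board would be unaware of treatment.** The trial is open-label and single-center, the investigator must be consulted, and the board includes the Principal Investigator or a deputy (9.10). It also reviews individual safety data before each second dose (9.4.1). The narrower fact is that the report's listed content omits antipyretic use.
- **That subjects may pre-medicate for day 28.** Section 9.4.9 gives no such permission, and subjects are on the ward from the evening before doses 1 and 2. Confinement does not cover the ambulatory third dose, but there too the text shows a wording gap and not a permission.

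What the reply does not answer is the order of reading and intake. That is a matter of data collection, and the protocol section that sets out the diary items is silent on it.

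**Conclusion.** The point holds as a measurement gap, not as a demonstrated bias. Antipyretics are permitted throughout the solicited window, and the listed diary items do not allow a temperature to be classed as taken before or after treatment. Later-onset fever, peak grade and duration can be understated as a result.

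The size is unknown. The protocol gives no fever rate, no rate of antipyretic use and no masked share, and masking could be near zero. Greater understatement at 10^8 pfu is a reasonable inference from symptom-driven use and dose-dependent reactions, but no figure in the protocol shows it. A reader might conclude that the dose difference must shrink; the calculation gives a large reduction only when unequal masking is put in. Summaries are descriptive and no confirmatory test is planned (9.8.1.3), so what is at stake is the description of reactogenicity and the information before the board.

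On use before dosing, the finding is only that 9.4.8, 9.3.2 and 9.4.9 do not fit together.

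**What to change.** 1. In 9.5.2.8.9, instruct that the daily temperature is read before any antipyretic or analgesic that day. Alternatively, record the clock time of the reading so that it can be linked to the drug record already required by 9.4.8.
2. Tabulate the number of subjects using antipyretics by dose level and injection, and add that count to the interim safety report described in 9.10.
3. Optionally, show a sensitivity summary of measured fever or antipyretic use beside measured fever. It would also count subjects who treated only headache or arm pain, so it should not replace the measured rate. This can sit in the SAP.
4. Reconcile 9.4.8, 9.3.2 and 9.4.9 so that one place states how analgesics and antipyretics before dosing are handled. Which rule applies is for the sponsor and the investigator; none is proposed here.

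The cost is one diary field or instruction, one table and a wording correction. Access to rescue medication is unchanged.

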9.4.10 Treatment Compliance

9.4.10.1 Admission to the study

Admission to the study will be effective upon the subject's arrival at the study ward. A subject will only be admitted to the study if all inclusion and none of the exclusion criteria are met. Should there be any doubts as to the state of health, a subject will not be admitted to the study.

Subjects who fail to make themselves available upon commencement of the study or who cannot participate for personal reasons will be considered as not admitted to the study. These will be replaced by back-up subjects who will be recruited in surplus.

9.4.10.2 Subject Identification

Screening numbers are to be assigned sequentially to all subjects as they consent to take part in the study. This will be a 3-digit number starting at 001. The subject number is assigned to subjects when they are enrolled into the study and according to appearance of the subjects. This will be a 3-digit number starting at 101. For screening failures, the screening number will be the identifying number used throughout the documentation. Subjects, who will replace a subject e.g. a withdrawn subject, will receive a screening number according to the above described scheme. In difference to the described subject number assignment, replacement subjects will receive a 3-digit subject number which will consist of the old subject number (of the subject which should be replaced) plus 100.

Allocation to a certain subject number will be done in successive order following screening and based on the subjects' availability.

The investigator will keep a record relating the subject numbers and the names of all subject (including the CTC North identification number) that have given their informed consent, to allow easy checking of data in subject files, when required. This record will also include the date of subject's enrolment and completion, as well as subjects who could not be included in the study for whatever reason.

9.4.10.3 Screening, Confinement and Ambulatory Visits

9.4.10.3.1 Confinement (Day -1 to Day 1 and Day 27 to Day 29)

The Subjects will be admitted to the study ward in the evening on Day -1 going through regular check-in procedures including an ID check, vital signs, an inclusion/exclusion check, an alcohol breath test and a urine drug, and pregnancy test. The Subjects will stay on the ward until the morning of Day 1 experiencing blood draws for immunogenicity analysis, documentation of occurrence of any injection site reaction, systemic events/reaction and adverse event questioning throughout the confinement period. Subjects will be dismissed at the earliest after the 24 h after vaccination and after subjects were trained on the use of the diary.

This schedule will be repeated in for the second vaccination on day 27 to day 29.

9.4.10.3.2 Screening

At the screening visit the following interventions will be performed:

- Informed Consent
- I/E Criteria
- Medical History/ Demographics
- Physical Examination
- Vital Signs/Temperature
- ECG
- Height and Weight
- Alcohol Breath Test
- Urine Drug Screen
- Urine Pregnancy Test
- HIV/HBV/HVC Serology
- Safety Laboratory (Urine/Blood)
- Troponin T

9.4.10.3.3 Confinement Day -1 to Day 1 and Day 27 to Day 29

During confinement the following interventions will be performed:

- I/E Criteria check
- Update medical history
- Targeted physical examination
- Vital signs / Temperature
- 12-lead ECG (only on day 28)
- Injection Site reaction & systemic events/reaction assessment
- AE/ConMed
- Alcohol Breath Test
- Urine Drug Screen

- Serum Pregnancy Test
- Safety Laboratory (Urine/Blood)
- Blood sampling for humoral immunogenicity
- Blood sampling for cellular response
- PBMC freezing and plasma aliquots
- Blood sampling for RNA storage (only on day 0, 1, 28, 29)
- Blood sampling for troponin (only on day 28)
- Blood sampling for innate immunity (only on day 0, 1, 28 and 29)
- Training on subject diary
- Collection and review of diary

After dosing the following events will be performed **at 2 h, 4 h, 6 h, 8 h, 12 h, 24 h**:

- Vital signs (and at 0 h, before dose administration)
- Temperature (and at 0 h, before dose administration)
- (AE)/ConMed (and at 0 h, before dose administration)
- Injection site reactions & systemic events/reactions assessment

9.4.10.3.4 Ambulatory Visits

Subjects will return to the study ward for ambulatory visits on study day 3, 7 and 14 (± 2), after the first vaccination and on study day 35, 42 (± 2), 56 (± 3), 84 (± 3) after the second vaccination. On the ambulatory visits the following events will be performed:

- Targeted Physical Examination (only on day 42)
- Vital signs/ Temperature
- 12-lead ECG (only on day 7, 14, 35, 42)
- Injection Site reaction & systemic events/ reaction assessment (only on day 3, 7, 14, 35 and 42)
- Safety Laboratory (Urine) (only on day 7, 14, 35, 42)
- Safety Laboratory (Blood) (only on day 3, 7, 14, 35, 42)
- Blood sampling for troponin (only on day 7, 14, 35, 42)
- Blood sampling for humoral immunogenicity (only on day 7, 14, 35, 42, 56, 84)
- Blood sampling for cellular response (only on day 14, 42, 56, 84)
- PBMC freezing and plasma aliquots
- Blood sampling for RNA storage (only on day 3, 7, 35)
- Blood sampling for innate immunity (only on day 3, 7, 35)
- Adverse events assessment
- Concomitant medication assessment
- Collection and review of diary

9.4.10.3.5 Ambulatory vaccination and subsequent ambulatory visits (only for subjects who gave consent to the study extension)

Subjects will return to the study ward for an ambulatory vaccination visit 12 months (± 4 months) after the first immunization.

The following interventions will be performed:

- Informed Consent
- I/E Criteria check
- Update medical history
- Weight
- Physical examination
- Vital signs / Temperature
- 12-lead ECG
- Injection Site reaction & systemic events/reaction assessment
- AE/ConMed
- Alcohol Breath Test
- Urine Drug Screen
- Urine Pregnancy Test
- Safety Laboratory (Urine/Blood)
- Blood sampling for humoral immunogenicity
- Blood sampling for cellular response
- PBMC freezing and plasma aliquots
- Blood sampling for RNA storage
- Blood sampling for troponin
- Blood sampling for innate immunity
- Dosing
- Training on subject diary

After dosing the following events will be performed **at 2 h, 4 h and 6 h**:

- Vital signs (and at 0 h, before dose administration)
- Temperature (and at 0 h, before dose administration)
- (AE)/ConMed (and at 0 h, before dose administration)
- Injection site reactions & systemic events/reactions assessment

Subjects will return to the study ward for ambulatory visits on study day 1, 3, 7 and 14 (± 2), after the third vaccination.

On the ambulatory visits the following events will be performed:

- Vital signs/ Temperature
- Injection Site reaction & systemic events/ reaction assessment
- Safety laboratory (urine) (only on day 7, 14)
- Safety laboratory (blood)
- Blood sampling for humoral immunogenicity (only on day 7, 14)
- Blood sampling for cellular response (only on day 7, 14)
- PBMC freezing and plasma aliquots
- Blood sampling for RNA storage (only on day 1, 3, 7)
- Blood sampling for innate immunity (only on day 1, 3, 7)

- Adverse events assessment
- Concomitant medication assessment
- Collection and review of diary

